
 
Assessment of postoperative liver function and regeneration:
 
Liver volumetry will be measured using image
 
J software downloaded from
 
http://rsbweb.nih.gov/ij/. The accuracy of this method was reported in a prior study.
 
Volumetric study will be performed based on CT scan studies obtained as standard of care preoperatively before each liver resection and at one and three months after each resection.
 
Collected data will be reported as percentage compared to the preoperative hepatic volume.
 
Specific Aim 2: To analyze the relationship between HO-1 induction and the quality of post-hepatectomy liver regeneration
 

 
2.1 Analyze the relationship between CO production and the quantity and quality of hepatic regeneration assessed by computed scans liver volumetric study at one and three months after PH and liver function tests.
 
2.2 Determine the relation between hepatic related morbidity in patients undergoing partial hepatectomy and their ability to induce HO-1
 

Study design: Aim 2.1: As CO is uniquely produced by HO reaction; its level was previously validated to check HO-1 induction. Checking this level and comparing outcome of the previously created three groups of patients (<25%, 25-50% and >50% PH) according to their ability to induce HO-1 after PH. Liver regeneration will be evaluated by radiological criteria at one and three months after PH as described above as well as laboratory criteria including liver function tests. Aim 2.2: HO-1 induction was found to offer beneficial protective effect in different clinical and surgical occasions. In this setting of PH, surgical complications in the perioperative (30 days) period graded by Clavien-Dindo Classification will be reported and analyzed regarding its relation with the ability to induce HO-1.
Procedures and Methods: Liver function tests routinely checked on daily basis till normalization will be monitored. This includes serum protein, Albumin, liver enzymes (AST and ALT), alkaline phosphatase and bilirubin level. The duration needed to this normalization will be checked as well as the trend of each of these laboratory parameters. Hepatic morbidity will be evaluated using the criteria used by the international study group of liver surgery being normalization of the INR and bilirubin by POD#5 while the severity

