#### Analyses:

All results will be collected in Excel Document. Analyses of groups based on the extent of liver resection and CO production. Results of different subgroups will be analyzed; comparison between groups will be performed by fisher test, paired and unpaired student t test, main Whitney test or ANOVA with repeated measurements when appropriate. Significance is defined as p<0.05.

Potential problems and alternative strategy: It is possible that HO-1 induction varies according to preoperative and intraoperative factors beside the patient own ability to induce HO-1. The most important known other factors are smoking and intraoperative blood transfusion will be reported in the study, however, other factors may exist and influence the result of this study. Preoperative factors may include preoperative use of chemotherapy and the presence of underlying liver cirrhosis. Intraoperative factors may include operative time and surgical technique (open or minimally invasive). In case of significance variance between patient s in the same group (same percentage of PH) Subgroup analysis including different variants (preoperative chemotherapy, perioperative

	blood transfusion and onen vorsus minimally
	blood transfusion and open versus minimally
	invasive technique) will be used to assess the
	effect of these factors.
Study Population:	125 participants enrolled locally; 125
	enrolled worldwide
Inclusion Criteria:	1-Patients plans to have partial liver
	resection for primary liver pathology or
	metastatic disease
	2-Patients able to comprehend and willing to
	sign the written consent form
Exclusion Criteria:	1-Patients with age less than 18 years
	2-Patients identified as part of the vulnerable
	populations as defined in the current
	application, except women with child bearing
	potential with negative pregnancy test
Study Treatment:	For Aim 1, after the patient's procedure, they
	will have to exhale into the device listed for
	collecting exhaled air specimen.
	For Aim 2, the patient's blood samples that
	are routinely collected after a hepatectomy
	will be used for analyzing serum protein,
	Albumin, AST and ALT, alkaline phosphatase,
	and bilirubin level.
	The duration of an individual's participation
	will be about 3 months +/- 2 weeks.
Study Procedures and Assessments:	Aim 1:
	Procedures and Methods
	- Protocol:
	For collecting exhaled air specimen, each
	patient will be instructed to exhale
	completely, and then

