#### 1. INTRODUCTION

Inducible Heme Oxygenase (HO - 1), an enzyme critical for heme catabolism, is also involved in cellular response to oxidative stress. We have previously shown that induction of HO-1 expression in response to limb ischemia confers pulmonary cellular protection against oxidative stress suggesting a systemic factor; however, the mechanism of this protection is unclear. Our follow-up study showing that carbon monoxide (CO) the product of heme catabolism by HO-1, can mimic this protection suggests that CO itself may be the important active molecule. Recent animal work has independently shown that HO-1 induction may also influence cellular regeneration in the liver following partial hepatectomy. Independently, CO has emerged as growth-promoting signal molecule with anti-apoptotic effect that protects hepatocytes from hypoglycemia - induced cytotoxicity. Further, administration of CO significantly improved the survival of mice after initiation of fulminant hepatitis and enhances rapid and early hepatocytes proliferation after partial hepatectomy, when mice lacking functional HO-1 were unable to mount an appropriate regenerative response. Collectively, these data suggest that the heme oxygenase - CO offers either direct or indirect protection against cellular injury and may promote regeneration in the liver. In this proposal, we will directly test the hypothesis that HO-1 induction is critical to hepatic regeneration after partial hepatectomy. We will further test the relevance of this observation in human patients undergoing partial hepatectomy by measuring CO production and correlating this to parameters of liver regeneration. To achieve objective, we will pursue two specific aims: (1) we will monitor the extent of HO-1 induction (by measuring endogenous CO production) in relationship to the extent of hepatic resection (2) we will assess the production of CO in patients following liver resection and correlate these findings to the rate of liver regeneration and liver function. This research will establish a framework for understanding the role of HO-1 induction in liver regeneration and will provide a foundation for developing more effective approaches in enhancing hepatic regeneration and preventing liver failure after partial hepatectomy.

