## 3. INVESTIGATIONAL PLAN

This is a University of Maryland Medical System multi-site study being done at University of Maryland Medical Center and UM Baltimore Washington Medical Center.

The study will monitor carbon monoxide production in patients undergoing liver resection and aims to identify the relationship between CO production and recovery after this resection.

Carbon monoxide will be checked from arterial blood gas obtained routinely as a part of the postoperative care as well as from the exhaled air of the patient through a CO detector commercially available and used as smokerlyzer helping people to stop smoking. The results of the surgical resection will be collected from the patient routinely ordered tests after liver resection including pathology of the resected part of the liver, laboratory and radiology tests.

The study duration for each individual patient is approximately 3 months +/- 2 weeks.

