# 6. STUDY VISITS

Patients planned to undergo partial hepatectomy for primary or metastatic hepatic pathology will be screened for eligibility to participate in this study. Objectives, methods of data

collection, and analysis will be discussed. After answering all patient questions and explaining the patient rights including refusal to participate, the patient will be offered to participate in the study. Patients who will accept to participate will be asked to sign the participation consent form. It is a prospective data collection without interference with the treatment plan.

For Aim 1, CO will be monitored before a patient's liver resection, and at 4- and 24-hours post-resection.

For Aim 2, CT scans of liver volume will be performed at one and three months posthepatectomy, as well as liver function tests PH.

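### The one-month regeneration volume is treated as a fixed occasion although routine-care CT dates will vary; a days-from-resection covariate would remove that noise (minor)

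*Combined protocol and SAP*

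**What the plan says.** The Protocol Summary (assessment of postoperative liver function and regeneration) bases volumetry on "CT scan studies obtained as standard of care preoperatively before each liver resection and at one and three months after each resection" and expresses the result as a percentage of preoperative volume. Section 3 confirms that outcome data come from "routinely ordered tests after liver resection including pathology of the resected part of the liver, laboratory and radiology tests". Section 6 says "CT scans of liver volume will be performed at one and three months posthepatectomy", but Sections 4 and 6 also describe prospective data collection that leaves treatment alone, so these are routine scans.

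Under Aim 2.1, "Liver regeneration will be evaluated by radiological criteria at one and three months after PH". Section 7 repeats the same two times. None of these places gives a day window. The only tolerance is in the Protocol Summary and Section 3: "The study duration for each individual patient is approximately 3 months +/- 2 weeks". It applies to total participation. It loosely bounds the three-month scan and says nothing about the one-month scan.

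The Analyses text plans "Analyses of groups based on the extent of liver resection and CO production", and "comparison between groups will be performed by fisher test, paired and unpaired student t test, main Whitney test or ANOVA with repeated measurements" when appropriate. It does not mention scan date or days from resection. The Introduction says the study will "correlate these findings to the rate of liver regeneration and liver function".

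**The concern.** A rate needs elapsed time, but the stated measure is a percentage at a nominal month. The named tests compare groups or fixed occasions, and none takes the day of the scan as an input. If the liver is still growing around one month, two patients with identical regrowth but different scan days receive different one-month volumes, and the gap widens with the extent of resection.

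At stake is precision in the one-month comparison of CO with regeneration. Timing scatter unrelated to CO becomes unexplained variance and can hide a real association. The scan date could account for it without further data collection from the patient.

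**Working it through.** The documents give no regrowth curve, volume SD, scan-date spread or power calculation, so there is no figure of the plan's to reproduce. Only the sample size (125) and the 0.05 level come from the protocol. Everything else below is assumed and varied.

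**Step 1: how far scan day can move a volume.** Let r be the remnant (% of preoperative volume), d the days from resection and h the half-time of regrowth toward an assumed 85% plateau:

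V(d) = 85 − (85 − r) × exp(−ln 2 × d / h)

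For r = 40, h = 14: V(44) − V(16) = 45 × (0.453 − 0.113) = 15.3 points.

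| Comparison | Remnant | h = 10 | h = 14 | h = 20 |
|---|---|---|---|---|
| Day 16 v 44 (±2 weeks) | 40% | 12.7 | 15.3 | 16.1 |
| Day 16 v 44 | 60% | 7.1 | 8.5 | 8.9 |
| Day 16 v 44 | 75% | 2.8 | 3.4 | 3.6 |
| Day 23 v 37 (±1 week) | 40% | 5.7 | 7.2 | 7.8 |
| Day 76 v 104 (three months ±2 weeks) | 40% | 0.2 | 0.8 | 2.0 |

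The ±2 weeks at one month is borrowed from the participation tolerance; the protocol does not set it. At three months the gap stays small (3.7 points even at h = 30).

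**Step 2: share of unexplained variance.** With r uniform on 40-80%, h = 14 and scan days uniform around day 30, the timing SD after adjusting for r is 2.66 points for ±14 days and 1.27 for ±7. The share is timing SD² / (timing SD² + residual SD²). For ±14 days at SD 3 it is 7.08 / (7.08 + 9) = 44%. At SD 5, 7, 10 and 15 it is 22%, 13%, 7% and 3%. For ±7 days it is 15% at SD 3 and 6% at SD 5.

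**Step 3: power without v with log days.** n = 125, standardised CO, half-time about 10% shorter per SD of CO, all models adjusted for r. The first two columns used 4,000 runs and the last 2,000, so simulation error is about 0.01 or less.

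| Residual SD | r 40-80%, ±14 days | r 40-80%, ±7 days | r 60-85%, ±14 days |
|---|---|---|---|
| 3 | 0.61 v 0.79 | 0.79 v 0.83 | 0.27 v 0.32 |
| 5 | 0.34 v 0.40 | 0.43 v 0.44 | 0.15 v 0.16 |
| 7 | 0.23 v 0.25 | 0.24 v 0.24 | no gain |
| 10 | 0.14 v 0.15 | 0.16 v 0.16 | no gain |
| 15 | 0.09 v 0.10 | 0.09 v 0.09 | no gain |

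The power levels reflect the assumed effect and do not estimate this study's power. Only the difference within a cell matters. With scan timing unrelated to CO and no CO effect, rejection rates were 0.044-0.058 for all models.

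**Step 4: a check without the curve.** For a constant slope of s points per week and scans uniform over ±w weeks, timing SD = s × w / √3, and required N rises by the factor 1 + timing SD² / SD². For slopes of 1-4, ±1-2 weeks and between-patient SD 10-15, the rise is 0.1% to 21%. The 21% corner is s = 4, w = 2, SD 10: 1 + 4.62² / 100 = 1.213. A slope of 4 for every patient is about the steepness of a 40% remnant throughout (16.1 points over 4 weeks). At a slope of 2, the same corner costs 5%.

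**The case against.** The strongest reply is that the documents establish no consequence, because every magnitude input is assumed. The clear loss sits in one corner of the grid: low residual SD, ±2 weeks and large resections. Remnants uniform on 40-80% put only 5/40, or one-eighth, of patients in the protocol's group with less than 25% resected. The fixed 85% plateau cannot represent the smallest resections at all. This stands, and it is why the size is given as a range.

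The reply continues that the word rate appears in the Introduction, whereas the operative Aim 2.1 concerns quantity and quality of regeneration at two nominal times, for which analysis by visit is ordinary. That is fair, but nominal-visit analysis still carries the timing noise. Nor does silence about dates commit the study to ignoring them: they are on the scans and could be used later. That is true too, and it makes the change cheap.

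A reader might infer three stronger things, none of which the documents support:

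- **Bias or false positives.** This needs scan timing to be linked to CO. One can imagine complications shifting scan dates and also relating to CO, but the protocol describes no such link. Any error rate computed from an assumed shift is hypothetical.
- **All regeneration outcomes are compromised.** On the assumed curve the three-month volume barely depends on scan day, and liver function tests do not depend on it at all.
- **One-month scans will run from day 16 to day 44.** Nothing says so.

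**Conclusion.** The point holds as a minor one. The one-month volume comes from scans whose dates the study does not control, and the listed tests treat it as a fixed occasion. If volume is still changing around one month, this adds noise to the one-month comparison of CO with regeneration.

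The loss is clear at residual SD 3-5 with ±2 weeks of scatter and large resections (power gain from the covariate 0.18 and 0.06). In the simulated mixed cohorts it is negligible at SD 10 or more. It is also about 0.01 or less from SD 5 up if scans fall within ±1 week or resections are mostly small; at SD 3 those two settings still show gains of 0.04 and 0.05. These figures rest on the assumed curve, scatter, case mix and effect size. The reason to act is that the covariate cost no material power in any setting tried.

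**What to change.** For the one-month volume, replace the listed group tests with a regression on CO that includes remnant percentage and log days from resection, taking the date from each CT. The remnant is already to be calculated from the preoperative CT under Aim 1.3. State this before the data are analysed.

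The cost is protocol wording, one extra covariate and slightly more analysis work, with no additional scans. The covariate removes the timing effect only; it does not adjust for any effect of complications on regrowth itself.

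Optional additions are:

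- a stated window for the one-month scan, which in a non-interfering study can classify scans but cannot make them punctual;
- a field for whether the CT was routine or prompted by a complication;
- a sensitivity analysis limited to in-window scans;
- a log days by remnant interaction, which added little (power 0.79 to 0.82 at SD 3, 0.40 to 0.42 at SD 5, nothing from SD 10).

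The three-month analysis can stay as planned.

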## 2. STUDY OBJECTIVE

The goal of this proposal is to elucidate the role of HO-1 induction in hepatic regeneration after partial hepatectomy (PH). There is a growing body of evidence that HO-1 induction through CO production has an important role in cellular protection and regeneration. To test this concept, we will monitor endogenous CO production in patients who undergo PH and analyze the relationship between CO production and hepatic regeneration. Using this approach, we will test the following two hypotheses: (1) HO-1 induction after PH is proportional to the extent of the surgical resection, and (2) failure to appropriately induce HO-1 is associated with impaired hepatic regeneration.

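### Aim 2.1 scores regeneration on a scale that carries the extent of resection; three resection bands remove most of the resulting bias, and continuous extent should be a covariate

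*Combined protocol and SAP*

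**What the plan says.** All references are to the combined protocol and SAP.

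- **Outcome scale.** The Protocol Summary (assessment of postoperative liver function and regeneration, repeated under Study Procedures and Assessments) says of CT volumetry: "Collected data will be reported as percentage compared to the preoperative hepatic volume".
- **Comparison.** The Aim 2.1 design text speaks of "comparing outcome of the previously created three groups of patients" (below 25%, 25-50% and above 50% resected) "according to their ability to induce HO-1 after PH". The Analyses text adds "Analyses of groups based on the extent of liver resection and CO production". No CO cut-off is given.
- **Tests.** "comparison between groups will be performed by fisher test, paired and unpaired student t test, main Whitney test or ANOVA with repeated measurements". No regression, analysis of covariance or other covariate model is listed.
- **Fallback.** If patients vary "in the same group (same percentage of PH"), subgroups by chemotherapy, transfusion and surgical technique are foreseen. Extent inside a band is not among them.
- **Hypotheses.** Section 2 states that "HO-1 induction after PH is proportional to the extent of the surgical resection". The second hypothesis links inadequate induction to poorer regeneration. Section 1 says only that the study will "correlate these findings to the rate of liver regeneration and liver function".
- **Source of extent.** Study Objectives, item 1.3, lists the one- and three-month scans among the measures of extent. The Aim 1.3 design text uses pre-resection CT (future liver remnant, FLR), the operative note and specimen weight. Study Endpoints assigns the post-operative scans to regeneration.

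**The concern.** A patient who loses more liver will, with the same proportional regrowth, show a lower percentage of pre-operative volume. If Hypothesis 1 is true, that patient also has higher CO. Extent then links high CO to a low regeneration score with no biological effect of CO on regrowth. Stratifying by three wide bands holds extent only roughly constant, and none of the listed tests uses it as a continuous quantity.

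At stake is the CT test of Hypothesis 2. Residual bias from extent could make CO look harmful or hide a real benefit. Variation in extent inside a band also adds noise. Because the text does not fix the comparison as within or across bands, that choice could be made after the data are seen.

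**Working it through.** **Inputs from the documents.** Sample size 125 (Study Population), band limits 25% and 50%, significance at p<0.05 (sidedness not stated; two-sided assumed). The 125 comes with no effect size, variance or power, so there is no calculation to reproduce. The documents give no regrowth share, CO-extent correlation or volumetry error; these are assumed below.

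**Algebra.** Let e be the fraction resected and k the share of it regrown. As a fraction of pre-operative volume:

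score = (1 - e) + ke = 1 - e(1 - k).

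This is free of e when k = 1, or when k rises with e enough to keep e(1 - k) constant.

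Inside the 25-50% band, with identical k for everyone:

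- k = 0.3: 1 - 0.25×0.7 = 82.5%; 1 - 0.50×0.7 = 65.0%; spread 17.5 points.
- k = 0.5: 1 - 0.25×0.5 = 87.5%; 1 - 0.50×0.5 = 75.0%; spread 12.5 points.
- k = 0.7: 1 - 0.25×0.3 = 92.5%; 1 - 0.50×0.3 = 85.0%; spread 7.5 points.
- k = 1: spread 0.

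**Main simulation.** n = 125; e from 5% to 80%, uniform or right-skewed; SD of k 0.15; correlation of CO with e 0.3 or 0.5; volumetry error SD 8 points. The score is regressed on CO, adjusting either for the three bands or for continuous e. False harm means a significant result against CO when CO has no effect (nominal 2.5%). Power is for a partial correlation of 0.3 between CO and regrowth share.

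| Regrowth share | False harm, bands | False harm, continuous e | Power, bands | Power, continuous e |
|---|---|---|---|---|
| mean 0.3-0.7, unrelated to e | 4-18% | 1-4% | 7-40% | 36-53% |
| mean 0.85, unrelated to e | 3-4% | 2-3% | 27-46% | 40-52% |
| mean 0.95, unrelated to e | not run | not run | 34-46% | 40-49% |
| rising with e, slope 0.6 | 3% | 2-3% | 35-50% | 39-50% |

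In the last row the false-harm runs used a mean share of 0.7.

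**Second simulation, different assumptions.** e uniform from 5% to 75%, volumetry error 4 points, true effect +0.06 in regrowth share per SD of the CO not explained by extent. At correlation 0.5 and mean share 0.5, bias per SD of CO was -5.07 points unadjusted and -0.75 with bands, so bands removed 1 - 0.75/5.07 = 85% of it. Two-sided type I error was 13.9% with bands and 5.0% with continuous e; power was 55% and 91%. With no CO-extent correlation there was no bias, but at mean share 0.3 bands still had 80% power against 90%.

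**Error in the extent measure (no CO effect).** With independent error in e of SD 5 points, false harm was 3-9% for continuous e and 5-28% for bands; at SD 10 points, 5-40% and 8-58%. The percentage resected and the outcome share the pre-operative volume as denominator, so error there enters both. With 10% shared error:

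- mean share 0.5: continuous 7-17%, bands 9-25%;
- mean share 0.7: continuous 8-15%, bands 8-18%;
- mean share 0.85: continuous 7-15%, bands 5-13%.

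**Mixing scales.** FLR% is the complement of percentage resected. Entering FLR% itself for 30% of patients and percentage resected for the rest gave false harm between 33% and 99%.

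**The case against.** The strongest reply is that the plan already controls extent. It forms three extent groups, compares outcome in those groups by CO induction, and elsewhere treats patients with the same percentage resected as one group. The reference in Hypothesis 2 to induction being appropriate points the same way. On that reading what remains is strata against a covariate, and the cost of strata is small when regrowth is nearly complete or rises with extent. Most of this stands. Within bands is the better reading, bands remove most of the bias, and the loss must be stated as conditional. But no passage fixes the comparison, and the sentence about the same percentage concerns variation in induction, not the regeneration test. Strata are also the weaker choice when the continuous measure is already being collected.

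A reader might infer more than the documents support:

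- **That the CT test is badly confounded.** Pooling CO across bands does give false harm of 34-100% under the main assumptions. The design text does not favour pooling; the main support for it is the word correlate in the Introduction.
- **That the bias always runs against CO.** If regrowth share rises steeply with extent (slope 1.0), the pooled error becomes false benefit (7-23%); with bands it is 3-5%.
- **That patients are put in the wrong band.** The design text does not form bands from the post-operative scans, so the conflict over objective 1.3 is one of wording.
- **That the liver function criterion is affected too.** The algebra concerns the CT measure only; liver function tests were not examined.

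**Conclusion.** The point holds in limited form. The CT score carries extent whenever regrowth is incomplete and larger resections do not catch up. Hypothesis 1 links CO to extent, and no listed test adjusts for extent beyond three bands. That much follows from the text and algebra alone. The size rests on assumptions, since only n = 125 is documented. With mean regrowth of 0.3-0.7 unrelated to extent, false harm with bands is modestly to clearly above nominal, and power can fall well below what the covariate model gives. At regrowth of 0.85 or above, or with a moderate rise in regrowth share with extent, the difference is small. The advantage of continuous extent also narrows, and can slightly reverse, when the pre-operative volume is measured with appreciable error. The conflict over objective 1.3 is real but minor.

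**What to change.** **(a) Analysis of Aim 2.1.** State that CO is compared at fixed extent. Model the one- and three-month CT volume (percentage of pre-operative) on CO, with continuous percentage resected as a covariate. Keep the three bands for description.

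Put extent on one scale for every patient. Use achieved percentage resected from specimen weight, with the weight-to-volume conversion stated. Where that is missing, use 100 minus FLR%, noting that this is planned rather than achieved extent. Do not enter FLR% itself in the same covariate.

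Add a sensitivity analysis for the shared denominator, for example absolute CT volume modelled on CO with pre-operative volume and specimen weight as separate covariates. In absolute terms the post-operative volume is pre-operative volume minus (1 - k) times the resected volume, so this form needs no ratio. It does not remove measurement error, but the same error no longer sits in the outcome and the covariate.

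**(b) Objective 1.3.** Reconcile it with the Aim 1.3 design text and Study Endpoints, so that extent comes from pre-resection CT/FLR, specimen weight and the operative report, and the post-operative scans measure regeneration.

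**Cost.** A wording change and one or two model degrees of freedom. FLR, specimen weight and the scans are already planned. Some residual confounding from measurement error will remain.
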